9.3.6. Covariates

Members of the study cohorts will be described according to claims-based covariates. Unless otherwise specified, diagnoses will be identified through the presence of ICD-10 codes, while prescription medications will be identified through pharmacy dispensings or administrations. No over-the-counter medications will be assessed. Drug use and disease status will be

² CPT copyright 2022 American Medical Association. All rights reserved.

categorized as yes (code present) or no (no code present). Demographic attributes will be determined on the cohort entry date while other factors will be assessed during the 365-day baseline period, unless otherwise specified. In addition to the covariates listed below, the 50 most common diagnoses, procedures, and medications will be described during the baseline period.

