9.3.6.2. Healthcare Utilization

- Number of outpatient visits;
- Number of emergency department visits;
- Number of 3-digit diagnosis codes;
- Number of drugs dispensed;
- Hospitalizations;
 - Number of hospitalizations;
 - Number of inpatient days (among patients who have been hospitalized).

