9.3.6.4. Treatment History

- Tofacitinib treatment;
 - Tofacitinib dose;
 - Average daily dose in prior 91 days;
 - Cumulative dose in prior 365 days;
 - Treatment duration;
- Zostavax[®] vaccination;
- TNF inhibitor treatment (eg, etanercept, adalimumab, golimumab, infliximab, certolizumab);
- Non-TNF biologics (eg, abatacept, rituximab, tocilizumab, sarilumab, anakinra, ustekinumab, vedolizumab);
- csDMARD treatment (eg, methotrexate, sulfasalazine, hydroxychloroquine, leflunomide, azathioprine);
- Immunosuppressants (eg, azathioprine, 6-mercaptopurine, cyclosporine);
- JAK inhibitor treatment (eg, baricitinib, upadacitinib);
- Corticosteroid treatment;
 - Average daily dose (eg, None, ≤ 5 mg/day, >5 to ≤ 10 mg/day, >10 to ≤ 20 mg/day, and >20 mg/day of prednisone average dose equivalent);
 - During 30 days prior to cohort entry;
 - During 365 days prior to cohort entry;
- Number of treatments for UC/RA prior to cohort entry;
- Chemotherapy;
- Radiotherapy;
- 5-aminosalicylates (eg, mesalamine, balsalazide, olsalazine);
- Ozanimod.

Additional therapies that are approved for the treatment of UC or RA may be incorporated if they become available. All of the above covariates may be considered for inclusion in the propensity score model used for IPTW.

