9.7. Data Analysis

9.7.1. Propensity Score Modeling

Propensity scores that discriminate between receipt and non-receipt of RZV will be created from a wide variety of baseline demographic, comorbidity, disease severity (based on proxies for disease severity, such as treatment with advanced therapy), and comedication indicators. The propensity scores will be used to calculate IPTW to adjust for potential confounding in the comparative analysis.

There will be 4 propensity score models that, separately, will estimate propensity scores that discriminate between (1) receipt of two doses of RZV and non-receipt of RZV in UC cohorts, (2) receipt of two doses of RZV and non-receipt of RZV in RA cohorts, (3) receipt of at least one dose of RZV and non-receipt of RZV in UC cohorts, and (4) receipt of at least one dose of RZV and non-receipt of RZV in RA cohorts. If there are confounders identified that would only be appropriate to include in one model and not the other, separate propensity score models for the outcomes HZ and disease flare will be considered.

Propensity score modeling will be performed to determine and analyze the predictors of RZV receipt, incorporating dozens of predictors of vaccination status (such as age, sex, comorbidities, and concomitant medications). Propensity scores will be estimated using logistic regression that includes predictors of vaccination, including pre-specified covariates (ie, covariates included in [Section 9.3.6.1 – 9.3.6.4](#)) and empirically identified covariates based on the most frequently occurring diagnoses, procedures, and medications dispensed, as independent variables in the model and receipt of 2 doses of RZV/non-receipt (or receipt of at least 1 dose of RZV/non-receipt) as the dependent variable. Only covariates assessed during the 365-day baseline period and known (or highly suspected) to be confounders will be included in the propensity score model. The list of empirically identified covariates will be reviewed, and those covariates that are known risk factors of HZ or UC/RA disease flares will be identified and considered for inclusion in the propensity score model. Those covariates that are correlates of RZV receipt but are not risk factors for the outcomes (and therefore not confounders) will be removed from consideration. Some pre-specified

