In addition, using the main study cohorts, Optum will consider applying a more restrictive definition of current tofacitinib exposure (ie, not including the 30-day grace period when identifying current tofacitinib users), and according to cumulative tofacitinib dose. To assess a potential dose-response relationship between tofacitinib exposure and study outcomes, a sensitivity analysis will be performed in which the cohorts are stratified based on tofacitinib dose. Specifically, the daily dose of tofacitinib will be calculated based on dispensings received in the 91 days prior to cohort entry and then the cohorts will be stratified according to high versus low dose of tofacitinib based on the median daily dose. In addition, the cohorts will also be stratified based on cumulative dose of tofacitinib received in the 365 days prior to cohort entry. As patient follow-up will not be censored upon discontinuation of tofacitinib treatment, a sensitivity analysis will be conducted in which patients are stratified based on continued exposure to tofacitinib during follow-up.

As the study period includes time before and during the COVID-19 pandemic, a sensitivity analysis will be conducted stratified by calendar time (cohort entry prior to 20 January 2020 and cohort entry on or after 20 January 2020).

A quantitative bias analysis will also be performed to assess the potential magnitude of bias due to unmeasured confounding, including confounding by incompletely captured or missing covariates (eg, UC/RA severity). A standard epidemiological spreadsheet will be used to assess the robustness of the results in the presence of an unmeasured confounder.³⁴ The results of the main analyses for the association between RZV exposure and the primary and secondary outcomes along with varying magnitudes of the confounder-outcome association and confounder-RZV association will be used to calculate the difference from the observed findings after accounting for the unmeasured confounder. The range of associations to be applied for the confounder-outcome and confounder-RZV associations will be informed by published literature and associations observed for related variables in the current study.

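### The covariate removal rule assumes that a correlate of vaccination that is not an outcome risk factor cannot be a confounder, which can screen out preventive-care markers that stand in for care seeking

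*Protocol*

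**What the plan says.** Protocol section 9.7.1 fills the propensity score models from two sources: the covariates pre-specified in sections 9.3.6.1 to 9.3.6.4, and covariates found empirically among frequent diagnoses, procedures and medications. Section 9.3.6 describes the empirical source: "the 50 most common diagnoses, procedures, and medications will be described during the baseline period".

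A general entry condition applies: "Only covariates assessed during the 365-day baseline period and known (or highly suspected) to be confounders will be included in the propensity score model". The empirical list is then filtered in two steps. The first picks out established risk factors: "The list of empirically identified covariates will be reviewed, and those covariates that are known risk factors of HZ or UC/RA disease flares will be" (the sentence ends by making these candidates for the model). The second step is the rule at issue: "Those covariates that are correlates of RZV receipt but are not risk factors for the outcomes (and therefore not confounders) will be removed".

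The pre-specified list includes utilization measures (section 9.3.6.2), beginning with "Number of outpatient visits" and going on to emergency visits, diagnosis-code and drug counts, and hospitalizations. Its only vaccine item is "Zostavax[®] vaccination" (section 9.3.6.4). It has no other vaccine, wellness visit or screening item. Section 9.3.6.4 adds: "All of the above covariates may be considered for inclusion in the propensity score model used for IPTW". For residual confounding, section 9.7.4 plans this: "A quantitative bias analysis will also be performed to assess the potential magnitude of bias due to unmeasured confounding".

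**The concern.** The rule treats two different kinds of variable as one. A variable that affects vaccination and has no other link to the outcome is an instrument, and dropping it is sound. A variable that does not cause the outcome but tracks an unmeasured trait driving both vaccination and the recorded outcome is a proxy confounder. Dropping it leaves bias that adjustment would have reduced. The parenthesis in the rule recognises only the first kind.

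This matters here because both outcomes exist only when a claim is filed. HZ is a single diagnosis code on one claim (section 9.3.5.1), and flare is built from dispensings, visits and procedures (section 9.3.5.2). Patients who seek more care may be vaccinated more often and also have more events coded. Patients who are healthier or more health-conscious may be vaccinated more often and have fewer events. The first mechanism lowers apparent effectiveness and raises the flare hazard ratio; the second does the reverse.

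Section 9.7.1 already accepts proxies for disease severity, such as advanced therapy. Its removal rule gives no matching route to proxies for health behaviour.

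**Working it through.** The protocol gives no figure on this point, so there is none to reproduce. Three checks follow.

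**1. Can Zostavax serve as the marker?** Section 9.5, Table 2, shows Zostavax claims in 16 of 649 recipients under 60 and 94 of 1,248 aged 60 or over: (16 + 94)/(649 + 1,248) = 110/1,897 = 5.8%. That is too rare to capture preventive-care behaviour. Any other such marker would have to come through the empirical list, which is where the rule applies.

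**2. Size of the bias with no other adjustment.** Assumed inputs, not from the protocol: preventive-care users make up p1 of vaccinees and p0 of comparators, and their recorded HZ rate is RR times that of other patients.

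Bias factor = (1 + p1(RR − 1)) / (1 + p0(RR − 1)). Apparent VE when the true VE is 70% = 1 − 0.30 × factor.

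| p1, p0 | RR | Factor | Apparent VE |
|---|---|---|---|
| 0.70, 0.45 | 0.8 | 0.86/0.91 = 0.945 | 71.7% |
| 0.80, 0.50 | 0.8 | 0.84/0.90 = 0.933 | 72.0% |
| 0.70, 0.45 | 1.2 | 1.14/1.09 = 1.046 | 68.6% |
| 0.80, 0.50 | 1.5 | 1.40/1.25 = 1.120 | 66.4% |

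If the same inputs held for flare, a true hazard ratio of 1.00 would read as 0.93 to 0.95 or 1.05 to 1.12. For scale, the two effectiveness thresholds interpreted in section 9.5, 66.7% and 70.8%, are 4.1 points apart.

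**3. Does keeping a non-causal marker help?** Let U be an unmeasured binary trait (prevalence 50%) that affects vaccination and recorded HZ. Let V be a marker that depends on U only and does not cause HZ. Comparators get the ATT weight of section 9.7.2, e/(1 − e), and true VE is set at 70.8%. All inputs on U and V are assumptions.

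One case in full: P(RZV | U = 1) = 0.30, P(RZV | U = 0) = 0.15, RR = 1.5.
- Share with U among vaccinees: 0.30/0.45 = 0.667. Among comparators: 0.70/1.55 = 0.452.
- V dropped: factor (1 + 0.5 × 0.667)/(1 + 0.5 × 0.452) = 1.333/1.226 = 1.088, so VE = 1 − 0.292 × 1.088 = 68.2%.
- Strong V kept (P(V | U) = 0.9 against 0.2): weighting raises the comparator share with U to 0.556. The factor is 1.333/1.278 = 1.043 and VE = 69.5%.
- Share of bias removed: (69.5 − 68.2)/(70.8 − 68.2) = 50%.

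The full set, with P(RZV | U) of 0.30/0.15 or 0.35/0.10:

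| Effect of U on recorded HZ | V dropped | Weak V kept (0.7/0.4) | Strong V kept (0.9/0.2) |
|---|---|---|---|
| RR 0.5 to 0.7 | 73.0% to 77.4% | 72.8% to 77.0% | 72.0% to 74.7% |
| RR 1.5 to 2.0 | 63.4% to 68.2% | 64.2% to 68.5% | 67.4% to 69.5% |

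Keeping V moves the estimate toward 70.8% in every scenario. A weak marker removes about a tenth of the bias and a strong one about 40% to 55%.

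**The case against.** A reader might infer that the protocol throws out other vaccines and leaves care seeking unadjusted. The documents do not support that. In context the rule filters only the empirical list. Visit, emergency, diagnosis-code, drug and hospitalization counts are pre-specified and enter by another route, although the wording that they may be considered leaves their inclusion not fully fixed. No section names a preventive-care marker for removal. Nor can the documents show that such markers are the best proxies available in claims; they are useful at most in proportion to how closely they track the trait.

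The rule can also be read leniently. If a risk factor means any predictor of the recorded outcome, or if a marker counts as a highly suspected confounder, it could stay. That reading is possible, but section 9.7.1 does not define the term, asks for known risk factors, and states the faulty inference outright. Two analysts could apply it in opposite ways.

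Eligibility narrows the contrast: everyone has 365 days of enrolment, full benefits, a UC or RA claim and current tofacitinib use. This stands, and with the utilization counts it makes the factors in check 2 ceilings.

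Other safeguards exist. Known confounders and imbalanced variables can enter the outcome models (sections 9.7.2 and 9.7.3), but a screened-out marker may not be among those examined. The bias analysis covers unmeasured confounding in general, with UC/RA severity as its example; it does not replace adjusting for something the claims may already hold. Further model detail may be in the SAP, but the rule itself is fixed in the protocol.

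**Conclusion.** The point holds in limited form. The step from not being a risk factor to not being a confounder is wrong for proxies of an unmeasured common cause. As worded, the rule can remove preventive-care markers that have no other route into the models. The aim of dropping pure correlates of vaccination is sound.

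The residual bias is probably modest and could go either way. The range of about 0.93 to 1.12 on the hazard ratio rests on assumed prevalences (70% to 80% against 45% to 50%) and rate ratios (0.8, or 1.2 to 1.5), and it ignores all other adjustment. The gain from keeping a marker depends on its strength and would be smaller where the utilization counts already capture the trait. This is an inexpensive improvement and does not threaten the design.

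**What to change.** In section 9.7.1:

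- Limit removal to variables judged to be pure predictors of vaccination (instruments), and delete the inference in the parenthesis.
- State that proxies of unmeasured common causes of vaccination and recorded outcome are kept, and record the reason for each variable removed.
- Pre-specify a short set of baseline preventive-care markers in all four propensity score models: influenza vaccination, pneumococcal vaccination, wellness visits and cancer screening.
- Exclude RZV claims and claims on the cohort entry date when building these markers. The baseline period in section 9.2.4 includes that date, which is the vaccination visit for RZV recipients and a randomly selected day for comparators.
- Use COVID-19 vaccination only for cohort entries in calendar periods when it was available, since accrual starts in October 2017.

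The cost is a few binary covariates and slightly more variable comparator weights. The balance checks and weight trimming already foreseen in section 9.7.2 would show whether the added variability matters.

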9.7.2. Inverse Probability of Treatment Weighting

The propensity scores will be used to calculate IPTW and weight each patient in the exposure cohorts. This will be performed separately for the RZV 2-Dose and RZV ≥ 1 Dose analyses. IPTW produces weighted groups that have similar patterns of the presence or absence of a large number of factors. With IPTW, the balance between the comparison cohorts can be expected to be similar to or better than would be achieved in a randomized trial with respect to all identified covariates. Matching on the propensity score will be considered as an alternative approach, but IPTW has the advantage that fewer eligible patients would be excluded due to their inability to match.

The IPTW will be defined such that the causal estimate is the average treatment effect in the treated (ATT).³² Two sets of IPTW will be estimated, one for the UC cohorts and one for the RA cohort. Briefly, to estimate the ATT, the weights are defined such that every RZV-exposed patient receives a weight of one, while the unexposed patients receive weights that are a function of the propensity score:

$$w_{ATT} = Z + \frac{e(1-Z)}{1-e}$$

where Z is the indicator for RZV exposure and e is the propensity score,

$$e = \Pr(Z = 1|X).$$

The propensity score is the probability of receiving RZV as a function of \mathbf{X} , a vector of the predictors of RZV exposure.

Balance of covariates among the IPT weighted cohorts will be assessed using the standardized difference (SD) comparing the weighted study cohorts. Any variables with an absolute SD >0.1 may be considered imbalanced. If specific variables remain imbalanced after weighting, they will be included as independent predictors in outcome models. Overall balance between the cohorts, both before and after weighting, will be assessed via overlap (or lack thereof) in histograms of the weights. Trimming of extreme weights will be considered.³³

9.7.3. Descriptive Analysis and Estimation of Risk

The report will include a flow chart depicting the number of patients that meet all study eligibility criteria. The study cohorts before and after IPTW will be described according to the baseline characteristics listed in Section 9.3.6.

9.7.3.1. RZV 2-Dose Analysis

The RZV 2-dose analysis will be used as the main analysis for assessment of the primary objective for effectiveness. Incidence rates and corresponding 95% confidence intervals for the primary outcome (HZ) will be calculated before and after weighting. All analyses will be performed separately within the UC and RA cohorts. The incidence rate of HZ in the RZV 2-Dose cohort will be compared to the Comparator 2-Dose cohort. Weighted Kaplan-Meier plots will be used to depict the cumulative probability of survival (non-occurrence of the event).

Given the sampling approach that will be utilized in this study (sampling with replacement), we will calculate the number of patients that were selected and included in a study cohort more than once (Section 9.2.3.2.1). If that number exceeds 10% of the study population, then covariance between observations will be taken into account using an appropriate method (eg, generalised estimating equations or robust variance estimators).

The relative hazard will be calculated through weighted Cox regression models with appropriate 95% confidence intervals. Known confounders that are strongly associated with RZV receipt and HZ may also be included in the regression models as well as any variables with an absolute SD >0.1 between weighted exposure cohorts. Additional details on model selection will be detailed in the SAP.

Patients will be further stratified by the following patient groups relative to their matched comparators:

1. Tofacitinib current users at time of receipt of first and second RZV doses;
2. Tofacitinib current users at time of receipt of second RZV dose only.

The first subgroup analysis conducted among patients who receive two doses of RZV and are current users of tofacitinib at the time of receipt of both doses will be the main comparison.

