Up to 2 comparators for each RZV initiator will be selected, matched on data source (ie, the Optum Research Database [ORD] or the Optum Medicare Advantage and Medicare Part D [MA-PD] Database) and other factors considered upon feasibility. Patients will be sampled with replacement. This process will be repeated for each 4-week window during the study period; as such, it is possible that a patient could be sampled as a comparator multiple times during the study. If patients are selected more than once into the study, it will be accounted for in the statistical analysis (Section 9.7.3).

Figure 4. Example of Time-Matched Vaccination Risk Sets in the RZV 2-Dose Analysis

If a patient selected for the comparator cohort subsequently receives RZV, their follow-up time within the comparator cohort will be censored upon the date of first administration of RZV. The patient may then be included in the RZV cohorts if they still meet all eligibility criteria. Consequently, patients are eligible to contribute person-time to the RZV cohort, the comparator cohort, or both the comparator cohort and (if subsequently vaccinated) the RZV cohort. Once a person contributes person-time to the RZV cohort, they are no longer eligible to contribute to the comparator cohort.

Patients with and without RZV exposure will be included in the UC RZV cohort and UC Comparator cohort, respectively, if they have at least one medical claim with a diagnosis of UC (International Classification of Diseases, 10th revision [ICD-10] code: K51*) in any position in the 365 days prior to and including their cohort entry date. Similarly, patients with and without RZV exposure will be included in the RA RZV cohort and RA Comparator cohort, respectively, if they have at least one medical claim with a diagnosis of RA (ICD-10 code: M05*) in any position in the 365 days prior to and including their cohort entry date. In addition, M06* (other rheumatoid arthritis) will also be used, except M06.1 (adult-onset Still’s disease) and M06.4 (inflammatory polyarthropathy). If a patient has claims with both UC and RA diagnoses in the 365 days prior to cohort entry, the claim closest to the cohort entry date will be used for cohort assignment.

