9.7.3.2. RZV ≥ 1 Dose Analysis

The RZV ≥ 1 dose analysis will be used to assess the secondary objectives for effectiveness and safety. Incidence rates and corresponding 95% confidence intervals for the primary (HZ) and secondary (disease flare) outcomes will be calculated before and after weighting in each of the 4 RZV ≥ 1 Dose and Comparator ≥ 1 Dose cohorts. All analyses will be performed separately within the UC and RA cohorts. The incidence rate of each outcome in the RZV ≥ 1 Dose cohort will be compared to the Comparator ≥ 1 Dose cohort. Weighted Kaplan-Meier plots will be used to depict the cumulative probability of survival (non-occurrence of the event).

As in the RZV 2-dose analysis (Section 9.7.3.1), we will calculate the number of patients that were selected and included in a study cohort more than once. If that number exceeds 10% of the study population, then covariance between observations will be taken into account using an appropriate method (eg, generalised estimating equations or robust variance estimators).

The relative hazard will be calculated through weighted Cox regression models with appropriate 95% confidence intervals. Known confounders that are strongly associated with receipt of at least one RZV dose and the study outcomes may also be included in the regression models as well as any variables with an absolute SD >0.1 between weighted exposure cohorts. Additional details on model selection will be detailed in the SAP

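### Correlation from repeat selection is handled only above a 10% trigger, although another section of the protocol promises it without condition

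*Protocol*

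**What the plan says.** Section 9.2.3.2.1.2 sets the sampling: "Patients will be sampled with replacement", afresh in each 4-week window and with up to two comparators per vaccinee. It then states: "If patients are selected more than once into the study, it will be accounted for in the statistical analysis", pointing to Section 9.7.3 for the method. The same section lets a comparator who is later vaccinated enter the RZV cohort.

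Section 9.7.3.1 counts the patients selected more than once and adds: "If that number exceeds 10% of the study population, then covariance between observations will be taken into account using an appropriate method". The examples given inside that branch are "eg, generalised estimating equations or robust variance estimators". Section 9.7.3.2 repeats the condition for the ≥1-dose analysis: "If that number exceeds 10% of the study population".

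A separate sentence covers the effect estimate: "The relative hazard will be calculated through weighted Cox regression models with appropriate 95% confidence intervals". It names no variance estimator. Section 9.7.2 defines the ATT weights (1 for vaccinees, e/(1−e) for comparators) and is also silent on variance.

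**The concern.** The two places disagree. One promises that repeat selection is always allowed for; the place it points to allows for it only above 10%. At or below 10%, following the stated rule means that two records of the same comparator with overlapping follow-up are treated as independent, so one HZ or flare event can count twice as if it came from two people.

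The threshold has no derivation, and it is not said whether the 10% is counted within the UC and RA cohorts separately, although all analyses are run separately in them. The choice of variance method is therefore left to a count seen only after sampling.

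Naming robust variance only in the above-10% branch also ties it to the wrong reason. Weighting by e/(1−e) calls for it even with no repeats. At stake are the confidence intervals for HZ and for flare.

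**Working it through.** **1. The plan's own precision figure (Section 9.5).** Inputs: 1.2 HZ cases per 100 person-years, 2:1 comparators, 2,000 or 4,000 exposed person-years.

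- 2,000 person-years, VE 66.7%: 2,000 × 0.012 × (1/3) = 8 exposed events; 4,000 × 0.012 = 48 comparator events. SE(log RR) = √(1/8 + 1/48) = 0.382. Upper VE limit = 1 − (1/3) × exp(−1.96 × 0.382) = 84.2%.
- 4,000 person-years, VE 70.8%: 14 and 96 events, SE 0.286, upper limit 83.4%.

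Both exclude 85% on Wald limits. Exact limits are 86.4% and 84.6%, so the stated thresholds are reproduced approximately, though no single method gives both. The calculation takes records as unweighted and independent. The 10% trigger has no calculation to reproduce.

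**2. Where the repeat share would fall.** Inputs from Table 1: 12,491 tofacitinib users, 1,932 with two RZV doses, 2,744 with at least one. Assumption: every pool member is equally likely to be drawn. With D draws from a pool of N, λ = D/N. Patients drawn at least twice = N[1 − e^(−λ)(1 + λ)]. Unique comparators = N(1 − e^(−λ)). Share = repeats / (vaccinees + unique comparators).

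| Analysis | Draws | Pool | Repeats | Unique comparators | Share |
|---|---|---|---|---|---|
| 2-dose | 2 × 1,932 = 3,864 | 12,491 | 488 | 3,323 | 488/5,255 = 9.3% |
| 2-dose | 3,864 | 12,491 − 1,932 = 10,559 | 556 | 3,236 | 556/5,168 = 10.8% |
| 2-dose | 3,864 | 12,491 − 2,744 = 9,747 | 591 | 3,190 | 591/5,122 = 11.5% |
| ≥1-dose | 2 × 2,744 = 5,488 | 12,491 | 905 | 4,442 | 905/7,186 = 12.6% |
| ≥1-dose | 5,488 | 9,747 | 1,071 | 4,196 | 1,071/6,940 = 15.4% |

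The two-dose analysis straddles the trigger, while the ≥1-dose analysis lies above it. Smaller two-dose pools of 8,000 and 4,000 would give 13.6% and 22.8%.

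**3. Effect of repeats alone on HZ.** If a repeated person's records share the same event, the comparator design effect is 1 + λ. For the 9,747 pool this is 1.40: SE = √(1/8 + 1.40/48) = 0.393 against 0.382, or +3%. For the 12,491 pool, the case below the trigger, it is 1.31: SE = 0.390, or +2%.

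**4. Effect of weights and repeats together.** Simulation with ATT weights, 2:1 records and the repeat share set at 9.9%, 1,500 runs per setting. The squared coefficient of variation (CV²) of the comparator weights and the flare rate of 0.4 per person-year are assumptions. Cells give SE, with coverage of the 95% interval in brackets.

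| Outcome | CV² | Model-based | Robust by record | Robust by person |
|---|---|---|---|---|
| HZ, 2,000 PY | 0.09 | 0.425 (96.9%) | 0.405 (95.3%) | 0.412 (95.9%) |
| HZ, 2,000 PY | 0.90 | 0.427 (93.8%) | 0.430 (93.5%) | 0.442 (94.3%) |
| HZ, 2,000 PY | 2.35 | 0.429 (91.6%) | 0.465 (92.9%) | 0.483 (94.1%) |
| Flare-like | 0.09 | 0.143 (96.6%) | 0.128 (94.5%) | 0.131 (95.1%) |
| Flare-like | 0.90 | 0.143 (93.6%) | 0.148 (94.1%) | 0.153 (94.9%) |
| Flare-like | 2.35 | 0.144 (85.8%) | 0.176 (93.1%) | 0.183 (94.0%) |

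The last two columns isolate the repeats: clustering by person raises the SE by about 2% to 4%. The model-based column shows what ignoring the weighting would do. The error is in either direction, and it is large only with highly variable weights. With no repeats at all, model-based coverage for HZ is already 96.8%, 95.0% and 91.5% at the three CV² values, so the weights are the main driver.

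Limits: constant hazards, known weights, at most two selections per person, second entry within 0.25 years, coverage taken around the mean estimate. Clustering is not perfect with few events: in the third row its SE is 0.483 against an empirical SD of 0.518.

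**The case against.** A reader might infer that the protocol commits to model-based intervals at or below 10%. It does not. The Cox sentence stands apart from the 10% rule and promises suitable intervals without naming an estimator, so a robust or bootstrap variance is neither specified nor excluded. The SAP, not shown here, may name one. The silence on the estimator is therefore not itself the fault, and the poor coverage in the model-based column is conditional on a choice that the document does not make.

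A reader might also infer that every interval is materially wrong, or that moving from comparator to RZV counts events twice. Neither is supported. Coverage for HZ stays near nominal at the two milder weight settings, and Section 9.7.2 says that trimming of extreme weights will be considered. A comparator who is vaccinated is censored at first RZV, so the two stretches of follow-up do not overlap. Flare follow-up stops at 90 days, so entries further apart than that cannot share a flare.

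Lastly, the trigger may well fire. Selection needs current use in the window, so longer-term users face more draws. If draw rates were exponentially distributed with the same mean (an assumption, λ = 0.366), the two-dose share would be 10,559 × (0.366/1.366)² = 758 over 1,932 + 2,829, or 15.9%. Covariance would then be handled.

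All of this limits the size of the problem. It does not remove the contradiction, and it gives no reason to keep the threshold.

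**Conclusion.** The point stands as a should-fix. Sections 9.7.3.1 and 9.7.3.2 do not deliver what Section 9.2.3.2.1.2 promises: at or below 10%, repeated comparator records with overlapping follow-up have no provision for their correlation. The equal-chance estimate of about 9% to 12% for the two-dose analysis means that the method could change with small shifts in the data and differ from the ≥1-dose analysis without statistical cause.

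The expected harm from repeats alone is small, about 3% on the HZ standard error. A serious loss of coverage, chiefly for flare, would need both highly variable weights and a variance that ignores them. The first is an assumption; the second is not stated in the protocol.

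**What to change.** Delete the 10% condition in Sections 9.7.3.1 and 9.7.3.2, which brings them into line with Section 9.2.3.2.1.2. State that every weighted rate and weighted Cox model uses a sandwich variance clustered on the unique person, across repeat selections and across comparator and RZV membership. A patient-level bootstrap that re-fits the propensity score in each resample is an acceptable alternative. Keep the count of repeat selections as a descriptive result.

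The cost is a wording change and a small programming change. No new data are needed, and almost nothing is lost when repeats are few.
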